5.2 Secondary Endpoints

- 5.2.1 Poor bleeding score (binary) at 1, 2, 3, 4 weeks, 12 weeks, and 1 year after study enrollment defined as WHO Bleeding Scale ≥ 2 or Modified Buchanan Scale ≥ 3
- 5.2.2 Cumulative number of rescue therapies required during the first 12 weeks of treatment
- 5.2.3 Platelet response (binary), defined as ≥ 3 of 4 weeks with platelets $>50 \times 10^9/L$ during weeks 6-12 of therapy, but patient required a rescue treatment during weeks 1-2 of study
- 5.2.4 No further need for treatment (binary) after 12 weeks or 6 months of study
- 5.2.5 Treatment response (binary endpoints) at 1 year defined as:
 - **CR** is defined as platelet count $>/= 150 \times 10^9/L$
 - **Primary Remission** at 1 year is defined as CR at 1 year with no second-line agents required and $>/= 3$ months after discontinuing most recent platelet active medication
 - **Disease resolution** at 1 year is defined as CR at 1 year $>/= 3$ months after discontinuing most recent platelet active medication. May have received a second-line therapy, excluding rituximab or splenectomy.
 - **Disease stability** at 1 year is defined as platelets $>/= 50 \times 10^9/L$ but $<150 \times 10^9/L$ $>/= 3$ months after discontinuing most recent platelet active medication.
- 5.2.6 Number of 2nd-line therapies (defined in section 7.2.1) in weeks 13-52
- 5.2.7 Absolute change in percentage of CD4⁺25⁺Foxp3⁺ regulatory T cells from baseline at 12 weeks and 1 year
- 5.2.8 Absolute change in parent proxy-reported KIT overall scores from baseline to 1 week, 4 weeks, 12 weeks, and 1 year after study enrollment (see Appendix A2)
- 5.2.9 Total scale intensity ratings (continuous) from the Hockenberry Fatigue Scale-Parent (FS-P) at 1 week, 4 weeks, 12 weeks, and 1 year (see Appendix A2)
- 5.2.10 Serum iron, TIBC, transferrin saturation, ferritin, MCV, and hemoglobin at 12 weeks, 6 months, and 1 year after study enrollment
- 5.2.11 Safety evaluations as defined by:
 - Abnormal LFTs:
 - ALT $\geq 3x$ ULN in patients with normal baseline
 - ALT $\geq 3x$ baseline or $\geq 5x$ ULN (whichever is lower) in patients with abnormal baseline
 - ALT $\geq 3x$ ULN AND bilirubin $\geq 1.5 \times$ ULN ($>35\%$ direct)

- Incidence of adverse events (see section 9.1.6)
- Incidence of serious adverse events (see section 12.2)

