3.2 Secondary Objectives

- 3.2.1 To compare the proportion of patients with poor bleeding scores (WHO Bleeding Scale \geq 2 or Modified Buchanan Score \geq 3) at 1, 2, 3, 4, 12 weeks and 1 year in patients with newly diagnosed ITP treated with eltrombopag vs. standard first-line agents
- 3.2.2 To compare the cumulative number of rescue therapies (defined in section 8.4) needed during the first 12 weeks of treatment for patients with newly diagnosed ITP treated with eltrombopag vs. those treated with standard first-line agents
- 3.2.3 To compare platelet response during weeks 6-12 of study in patients treated with eltrombopag vs standard first line agents who required a rescue treatment during weeks 1-2 of study
- 3.2.4 To compare the proportion of patients who do not need ongoing treatment at 12 weeks and 6 months for patients with newly diagnosed ITP treated with eltrombopag vs. those treated with standard first-line agents
- 3.2.5 To compare the proportion of patients with a treatment response (4 binary endpoints (section 5.2.5)) at one year after study enrollment in patients with newly diagnosed ITP treated with eltrombopag vs. those treated with standard first-line agents
- 3.2.6 To compare the number of 2nd-line therapies (defined in section 7.2.1) used in weeks 13-52 for patients with newly diagnosed with ITP treated with eltrombopag vs. those treated with standard first-line agents
- 3.2.7 To compare the absolute change in percentage of CD4 $^{+}$ 25 $^{+}$ Foxp3 $^{+}$ regulatory T cells (Tregs) a) from baseline to 12 weeks; and b) from baseline to 1 year, in patients with newly diagnosed ITP treated with eltrombopag vs. those treated with standard first-line agents
- 3.2.8 To compare change in Health Related Quality of Life (HRQoL) from a) baseline to 1 week, b) baseline to 4 weeks, c) baseline to 12 weeks, and, d) baseline to 1 year, as measured by the parent-proxy report of the Kids ITP tools (KIT) and Global Change Scale for patients with newly diagnosed ITP treated with eltrombopag vs. those treated with standard first-line agents
- 3.2.9 To compare fatigue at 1 week, 4 weeks, 12 weeks, and 1 year as measured by the parent-proxy report of the Hockenberry Fatigue Scale-Parent (FS-P)

for patients with newly diagnosed ITP treated with eltrombopag vs. those treated with standard first-line agents

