To address secondary objective 3.2.2, an ANCOVA model will be used to compare the number of rescue therapies between the two arms.

To address secondary objective 3.2.3, the observed proportion and 95% confidence interval of platelet responders will be calculated in the subset of patients who required a rescue treatment during weeks 1-2 of the study.

To address secondary objective 3.2.4, the Cochran-Mantel-Haenszel test will be used to compare the proportion of patients who do not need ongoing treatment at 12 weeks and 6 months between the two arms.

To address secondary objective 3.2.5, the Cochran-Mantel-Haenszel test will be used to compare the proportion of patients with a treatment response at one year between the two arms.

To address secondary objective 3.2.6, an ANCOVA model will be used to compare the number of 2nd-line therapies between the two arms

To address secondary objective 3.2.7, an ANCOVA model will be used to compare the absolute change from baseline in percentage of regulatory T cells at 12 weeks and 1 year between the two arms

To address secondary objective 3.2.8, KIT scores will be calculated as per the methods described in Klaassen et al.²⁸ Spaghetti plots will be used to visualize the KIT scores over time per patient by treatment arm. An ANCOVA model will be used to compare the absolute change from baseline in KIT overall score at 1 week, 4 weeks, 12 weeks, and 1 year between the two arms. An ANCOVA model will be used to compare the Change Scale score at 1 week, 4 weeks, 12 weeks, and 1 year between the two arms.

To address secondary objective 3.2.9, fatigue scores will be calculated as per the methods described in Hockenberry et al.²⁹ All measures will be rescaled from 0 (no fatigue) to 100 (high fatigue) for consistency in scoring. Spaghetti plots will be used to visualize the fatigue scores over time per patient by treatment arm. The PROMIS tired question: “My child (I) got tired easily never to almost always” will be used as an anchor with severe fatigue defined as “often” or “almost always” with moderate fatigue being “sometimes”. An ANCOVA model will be used to compare the absolute change from baseline in fatigue at 1 week, 4 weeks, 12 weeks, and 1 year between the two arms.

To address secondary objective 3.2.10, an ANCOVA model will be used to compare iron indices at 12 weeks, 6 months, and 1 year between the two arms

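### Disease stability at 1 year is capped below 150 × 10⁹/L, so a lower proportion can mean more remissions or more failures and the planned test cannot be read alone

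*Combined protocol and SAP*

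**What the plan says.** Secondary objective 3.2.5 is "To compare the proportion of patients with a treatment response (4 binary endpoints (section 5.2.5)) at one year after study enrollment". Section 5.2.5 introduces the set as "Treatment response (binary endpoints) at 1 year defined as" and then lists complete response (CR, a count of at least 150 × 10⁹/L), primary remission, disease resolution and disease stability.

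- Primary remission and resolution both build on CR; the latter begins "Disease resolution at 1 year is defined as CR at 1 year". Both add a requirement of at least 3 months since the last platelet-active medication. None of these three endpoints has an upper limit.
- Stability ("Disease stability at 1 year is defined as platelets" and so on) requires a count of at least 50 but below 150, with the same 3 months off medication. It is the only one of the four with a ceiling.

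For objective 3.2.5, section 16.c says that "the Cochran-Mantel-Haenszel test will be used to compare the proportion of patients with a treatment response at one year between the two arms". Fisher's exact test is the fallback, and the analysis set is the evaluable patients. The plan does not order the four categories and has no combined endpoint of 50 or more at 1 year. It does not restrict stability to patients without CR or say how a lower stability proportion is to be read. It states no sidedness or significance level for these tests.

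**The concern.** A binary response endpoint should have a better and a worse side. On stability, a child off drug with a count of 160 scores no, and so does a child with a count of 10. The proportion falls when children remit and also when they fail, so the sign of the arm difference does not show which happened.

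This matters because of what the protocol hopes to see. Section 2.2 expects most newly diagnosed patients to resolve within a year, and section 1 suggests that early eltrombopag may change how many do. If it moves children from the 50 to below 150 band to 150 or more, the stability comparison moves against the drug because the drug worked. A table of four treatment-response tests could then contain one row that appears to favour standard therapy.

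**Working it through.** **Structure, with no assumption.** Off medication for at least 3 months, the scoring under 5.2.5 is:

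| Count (× 10⁹/L) | CR | Stability |
|---|---|---|
| below 50 | no | no |
| 50 to below 150 | no | yes |
| 150 or more | yes | no |

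The worst and best rows score alike on stability.

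**Size.** The plan states no expected rate and no power for any 1-year endpoint, so there is no figure to reproduce. The inputs from the plan are the maximum sample of 162, randomized 2:1 as 108 and 54, in six strata of at most 27 (18 and 9). The 1-year rates and the two-sided 0.05 level are assumptions.

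With p₁ the standard-arm and p₂ the eltrombopag-arm stability rate, and p̄ their pooled value, the expected z is (p₂ − p₁) / √[p̄(1 − p̄)(1/54 + 1/108)].

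For 35% against 20%:
- p̄ = (54 × 0.35 + 108 × 0.20)/162 = 40.5/162 = 0.25.
- Standard error = √(0.1875 × 0.02778) = 0.0722.
- z = −0.15/0.0722 = −2.08.
- The exact binomial probability that z falls below −1.96 is 54.3%.

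The other rows come from simulating the stratified CMH test. The pooled normal approximation at 108 and 54 agrees to within about one percentage point. Rates are percentages with a count of 150 or more off drug / in the stability band / neither.

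| Standard | Eltrombopag | Eltrombopag significantly worse on stability | Significantly better on 150 or more |
|---|---|---|---|
| 50/20/30 | 65/15/20 | 13% | 45% |
| 40/30/30 | 60/20/20 | 30% | 68% |
| 30/35/35 | 50/20/30 | 54% | 69% |
| 40/30/30 | 65/15/20 | 61% | 86% |
| 50/25/25 | 75/10/15 | 70% | 89% |
| 30/20/50 | 40/30/30 | under 0.1% | 23% |

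In every row eltrombopag has more patients at 150 or more and fewer in neither category. The reversal appears when more patients leave the band upward than enter it from below. In the last row the band gains instead, and eltrombopag tests significantly better on stability in 26% of trials.

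A single data set shows the same thing. With 16/108 (14.8%) against 16/54 (29.6%), z = −2.23 and two-sided p = 0.026; Fisher's exact p = 0.036.

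**Without the ceiling.** Adding the first two figures gives the rate of 50 or more off drug. For the third row this is 65% against 70%, and eltrombopag tests significantly worse in 0.5% of trials. For the fourth (70% against 80%) and fifth (75% against 85%) the figure is about 0.04% and 0.03%. The fourth and fifth rows have 30% and 35% power in the right direction, so removing the ceiling fixes the direction but does not give a strong test.

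**The case against.** The strongest case on the other side has five parts.

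- **The size is assumed.** The plan gives no 1-year rates, and the reversal depends on net movement out of the top of the band. This stands: only the range can be reported.
- **The full 162 may not be available.** The plan expects about 9% to withdraw early. At the 98 and 49 informative patients that it projects, the 54% becomes 51% (45% with Fisher's test). This stands, but changes little.
- **A significant reversal needs a two-sided test.** Sidedness is not stated for secondary endpoints, and the primary test is one-sided. Under a one-sided superiority test the endpoint would be non-significant, not reversed. This stands. The result would still be uninformative, since non-significance would again not separate remission from failure.
- **CR and resolution are reported beside stability.** A reader of all four rows could often see the cause. In the two scenarios with the highest reversal rates, CR is significantly better in 86% and 89% of trials. One might infer that the stability comparison has no meaning at all. That goes too far: comparing the share of patients in one category is valid, but it is not interpretable alone as benefit or harm.
- **A lower eltrombopag share may have another cause.** Table 8C keeps patients with counts from 30 to below 100 on their current dose, and some may stay on drug until 1 year. They cannot qualify as stable whatever their count. This stands, and removing the ceiling does not cure it.

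Reading 3.2.5 as one pooled response would soften the problem, but the objective's own wording specifies four binary endpoints.

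**Conclusion.** The definition is faulty for a tested response endpoint, and that conclusion rests on the text of 3.2.5, 5.2.5 and 16.c alone. How often it would mislead rests on assumed 1-year rates, 108 and 54 patients, and a two-sided 0.05 test. Under those assumptions a better arm tests significantly worse in about 13% to 70% of trials when patients move up out of the band, and in under 0.1% when the band gains from below.

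A reader might infer that the trial is likely to declare eltrombopag inferior, or that its main result is at risk. The documents support neither. Section 16.b rests the superiority conclusion on the primary platelet response alone, that endpoint has no upper limit, and no decision rule is attached to stability. The risk is that one secondary result is misread.

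**What to change.** In 5.2.5, define the tested endpoint as a platelet count of at least 50 × 10⁹/L with no upper limit, at least 3 months after the last platelet-active medication. Report the 50 to below 150 band descriptively beside resolution. This is a wording change and uses data already collected.

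Alternatively, analyse below 50, 50 to below 150, and 150 or more off drug as one ordered outcome. This also requires changing the 3.2.5 analysis in 16.c, because CMH on a binary proportion would no longer be the stated method.

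State the sidedness of the test with either option. Both still depend on 3 months off medication, so patients still taking eltrombopag late in the year cannot qualify. The plan should say that the result will be interpreted with that in mind, and the number of such patients should be shown by arm.

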5.3 Exploratory Endpoints

5.3.1 Platelet-specific endpoints

- Time to response (platelets $>30 \times 10^9/L$, and at least 2-fold increase in the baseline count and absence of bleeding) (IWG definition)¹⁷
- Treatment response (platelets $>30 \times 10^9/L$, and at least 2-fold increase in the baseline count and absence of bleeding) (IWG definition) at 12 weeks
- Time to platelet count $>100 \times 10^9/L$ and absence of bleeding (IWG definition)
- Treatment response (platelet count $>100 \times 10^9/L$ and absence of bleeding) (IWG definition) at 12 weeks
- Loss of treatment response (platelet count below $30 \times 10^9/L$, or less than 2-fold increase in the baseline count or bleeding) (IWG definition) at any time during the study period after achieving response during the first 12 weeks
- Extreme thrombocytosis (platelets $>1 \times 10^{12}/L$)

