< 50 x 10⁹/L following at least 2 weeks of eltrombopag	
Increase daily dose by 25 mg to a maximum of 75 mg/day.
 
For patients taking 12.5 mg once daily, increase the dose to 25 mg daily before increasing the dose amount by 25 mg.

≥ 50 x 10⁹/L to < 200 x 10⁹/L	Continue current dose
≥ 200 x 10⁹/L to ≤ 400 x 10⁹/L at any time	
Decrease the daily dose by 25 mg. Wait 2 weeks to assess the effects of this and any subsequent dose adjustments.
 
For patients taking 25 mg once daily, decrease the dose to 12.5 mg once daily.
 
For patients taking 12.5 mg once daily, discontinue eltrombopag.

> 400 x 10⁹/L at any time	
Hold eltrombopag; increase the frequency of platelet monitoring to twice weekly.
 
Once the platelet count is < 200 x 10⁹/L, reinitiate therapy at a daily dose reduced by 25 mg. For patients taking 25 mg once daily, reinitiate therapy at a daily dose of 12.5 mg.
 
If platelets remain ≥ 200 x 10⁹/L to <400 x 10⁹/L after 2 weeks, decrease frequency of platelet checks to weekly.

> 400 x 10⁹/L after 2 weeks of therapy at lowest dose of eltrombopag	
Discontinue eltrombopag.
 
If platelets drop to <50 x 10⁹/L after discontinuing eltrombopag, restart at the last effective dose (lowest dose that achieved platelet count ≥ 50 x 10⁹/L)

Please note: while platelets are checked weekly per study requirements, adjustments are made at time intervals described in the table

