8.2.2.4 Weaning weeks 13-52

For patients who have completed 12 weeks of eltrombopag and maintain a platelet count $\geq 100 \times 10^9/L$, eltrombopag will be weaned, by dose reducing 12.5mg q2 weeks per guidelines in table 8C below (with treating physicians exercising clinical judgement with respect to wean in the context of the patient's status, including intercurrent infections).

Patients who have been unable to be weaned off of eltrombopag by 1 year will discontinue study drug. Continuation on commercially available eltrombopag at that point is at the discretion of the investigator.

Table 8C Modified dose adjustment during weeks 13-52 of study

PLATELET COUNT RESULT	DOSE ADJUSTMENT OR RESPONSE
$< 30 \times 10^9/L$ 2 weeks after dose adjustment	Increase dose to last effective dose (to attain platelet count $\geq 30 \times 10^9/L$)
$\geq 30 \times 10^9/L$ to $< 100 \times 10^9/L$	Continue current dose.
$\geq 100 \times 10^9/L$ to $< 200 \times 10^9/L$	Decrease daily dose by 12.5 mg. Wait 2 weeks to assess the effects of this and any subsequent dose adjustments. If platelets remain $\geq 100 \times 10^9/L$ after 2 weeks at lowest dose, discontinue eltrombopag.
$\geq 200 \times 10^9/L$ to $\leq 400 \times 10^9/L$	Decrease the daily dose by 25 mg. Wait 2 weeks to assess the effects of this and any subsequent dose adjustments. For patients taking 25 mg once daily, decrease the dose to 12.5 mg once daily. For patients taking 12.5 mg once daily, discontinue eltrombopag.
$> 400 \times 10^9/L$	Discontinue eltrombopag
$< 30 \times 10^9/L$ after weaning off eltrombopag	Restart at the last effective dose (lowest dose prior to weaning). If platelets remain $< 30 \times 10^9/L$, increase per initial dose adjustment.

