9 STUDY PROCEDURES AND GUIDELINES

EVALUATIONS ¹ WEEK 0-12	SCREENING/DAY 0									UNSCHEDULED VISITS ¹⁰
		72H	W1	W2	W3	W4	W6	W8	W10	
ELIGIBILITY CHECKLIST	x									
PHYSICAL EXAM	x	x ²		x ²				x ²	x	
BLEEDING ASSESSMENT	x	x	x ³	x ³	x			x	x	
TELEPHONE VISIT			x	x						
DEMOGRAPHIC FORM	x									
BASELINE FORM	x									
CONCOMITANT MEDICATIONS	x	x		x			x	x		
OPHTHALMIC ASSESSMENT	x				As needed					
30 DAY FOLLOW-UP ⁴				As needed						
AE/SAE FORM				As needed						
RESCUE MED FORM				As needed						
HRQOL: KIT	x	x		x			x			
HOCKENBERRY FATIGUE SCORE	x	x		x			x			
PROMIS	x						x			
GLOBAL RATE OF CHANGE		x		x			x			
PLATELET COUNT ^{5, 6}	x	x	x	x	x	x	x	x	x ⁶	
CBC ⁵	x				x			x	x	
AST, ALT, TBILI ⁵	x ⁷		x ⁸		x ⁸	x ⁸	x ⁸	x ⁸	x	
DIR COOMBS	x ⁷									
LDH, RETIC ⁵	x ⁷						x			
CREATININE	x ⁷									
PREGNANCY TEST ⁵	x ⁷			x ⁸			x			
FE, TIBC, %SAT FERRITIN ⁵	x ⁷						x			

TREGS ⁹	x	x
SAMPLES FOR BANKING (OPTIONAL)	x	x

¹ 72H time point may occur +/- 24h. Week 1 – Week 4 procedures may occur +/- 72h.

Week 6 – Week 12 procedures may occur +/- 1 week, as long as procedures are separated by at least 1 week:

² Visits may be performed via telehealth when clinically appropriate if necessary for pandemic-related safety or research restrictions

³ Telephone administration of modified Buchanan scale

⁴ Patients will be followed for safety 30 days after the last dose of study treatment

⁵ Local labs (performed at outside lab not associated with ICON site) are acceptable for labs obtained between study visits

⁶ All platelet counts during Week 5 – Week 12 should be reported. Additional platelet measurements between the scheduled Week 6, 8, 10, and 12 measurements should be reported as unscheduled visits.

⁷ May use previously obtained values for screening assessments if done within past 7 days

⁸ Patients on eltrombopag arm only (for duration of eltrombopag administration)

⁹ Performed at central study lab

¹⁰Physical Exam, Bleeding Assessment, Concomitant Medications, Platelet count, and/or CBC to be performed at unscheduled visits when applicable

EVALUATIONS ¹ 4 MOS – 1 YR	4 MOS ²	5 MOS ²	6 MOS	7 MOS ²	8 MOS ²	9 MOS ²	10 MOS ²	11 MOS ²	1 YEAR	UNSCHEDULED VISITS ⁹
PHYSICAL EXAM			x ³				x ³	x		
BLEEDING ASSESSMENT							x	x		
CONCOMITANT MEDICATIONS			x				x	x		
OPHTHALMIC ASSESSMENT					As needed					
AE/SAE FORM					As needed					
RESCUE MED FORM					As needed					
30-DAY FOLLOW-UP ⁴					As needed					

END OF STUDY FORM	x ⁵									
HRQOL: KIT	x									

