HOCKENBERRY FATIGUE SCORE	x									
PROMIS	x									
GLOBAL RATE OF CHANGE	x									
PLATELET COUNT⁶	x ⁷	x ⁷	x	x ⁷	x	x				
CBC⁶			x						x	x
AST, ALT, TBILI⁶	x ⁷									
PREGNANCY TEST⁶		x ⁷		x ⁷		x ⁷		x ⁷		
FE, TIBC, %SAT FERRITIN⁶			x						x	
TREGS⁸									x	
SAMPLES FOR BANKING (OPTIONAL)	x									

¹ 6 month procedures may occur +/- 14 days. 1 year procedures may occur +/- 4 weeks

² Timepoint +/- 7 days

³ Visits may be performed via telehealth when clinically appropriate if necessary for pandemic-related safety or research restrictions

⁴ Patients will be followed for safety for 30 days after the last dose of study treatment

⁵ Form should be completed earlier if patient exits study prior to 1 year

⁶ Local labs (performed at outside lab not associated with ICON site) are acceptable for labs obtained between study visits

⁷ Patients on eltrombopag arm only (for duration of eltrombopag administration)

⁸ Performed at central study lab

⁹Physical Exam, Bleeding Assessment, Concomitant Medications, Platelet count, and/or CBC to be performed at unscheduled visits when applicable

All study assessments should be completed for patients enrolled on the study, even if subjects discontinue protocol treatment early (including patients on eltrombopag arm who discontinue eltrombopag due to non-response and patients on the standard therapy arm who receive prohibited therapies during weeks 1-12).

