To address secondary objective 3.2.11, the frequency and proportion (with 95% confidence interval) of patients with abnormal LFTs will be calculated. Adverse event rates will be coded by body system and MedDra classification term. Adverse events and serious adverse events will be tabulated by treatment group and will include the number of patients for whom the event occurred, the rate of occurrence, and the severity and relationship to study drug. If a patient experiences the same toxicity multiple times, a patient will be counted only once for a given toxicity at the maximum grade.

d. Analysis of Exploratory Objectives

Exploratory objectives are hypothesis-generating only. Any exploratory findings need to be confirmed in an independent study.

To address the platelet exploratory objectives 3.3.1, a Cochran-Mantel-Haenszel test will be used to compare the proportion of patients between treatment arms with: (1) specific platelet-defined treatment response at 12 weeks, (2) extreme thrombocytosis, and (3) loss of treatment response (in the subgroup of patients who achieved treatment response during the first 12 weeks. Cumulative incidence curves by treatment arm will be created to describe: (1) time to response and (2) time to platelet and bleeding response. Gray's test will be used to compare the cumulative incidence between treatment arms.

To address the patient-reported outcomes exploratory objectives 3.3.2, KIT scores and fatigue scores will be calculated as described. Spaghetti plots will be used to visualize the scores over time per patient by treatment arm. An ANCOVA model will be used to compare the absolute change from baseline at 1 week, 4 weeks, 12 weeks, and 1 year between the two arms.

To analyze the non-survey endpoints of exploratory objective 3.3.3, a Cochran-Mantel-Haenszel test (for categorical outcomes) or an ANCOVA model (for

continuous outcomes, like the cost of therapy) will be used to compare the two arms.

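### Loss of response at any time is compared between arms, but after Week 12 extra platelet counts are scheduled only on eltrombopag, so equal temporary losses would be detected more often in that arm

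*Combined protocol and SAP*

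**What the plan says.** - **Endpoint (Section 5.3.1).** A patient who responded in the first 12 weeks has lost response if any one of three things is seen: "platelet count below $30 \times 10^9/L$, or less than 2-fold increase in the baseline count or bleeding". It counts "at any time during the study period after achieving response during the first 12 weeks", so a single temporary dip qualifies and losses within Weeks 1–12 count too.
- **Analysis (Section 16.d).** A CMH test compares the arms on "loss of treatment response (in the subgroup of patients who achieved treatment response during the first 12 weeks". No common set of visits, interval-censored method or sensitivity analysis is given for this endpoint. The same section says: "Exploratory objectives are hypothesis-generating only".
- **Schedule after Week 12 (Section 9, 4 months to 1 year).** Footnote 7 restricts the monthly platelet counts: "Patients on eltrombopag arm only (for duration of eltrombopag administration". The 6-month and 1-year counts carry no restriction. Unscheduled visits may include a platelet count and bleeding assessment in either arm.
- **Schedule to Week 12 (Section 9).** The platelet visits from 72 hours to Week 12 are the same in both arms, and "All platelet counts during Week 5 – Week 12 should be reported".
- **Dose rules (eltrombopag only).** Table 8B says, while drug is held for a high count, to "increase the frequency of platelet monitoring to twice weekly". Table 8C says "Wait 2 weeks to assess the effects of this and any subsequent dose adjustments", which implies further counts after Week 12.
- **Bleeding (Section 9.1.5).** Scheduled assessments are not arm-specific. After baseline they fall at Weeks 1–4, Week 12 and 1 year, with none at 6 months.

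**The concern.** The proportion of patients in whom an event is ever seen rises with the number of times they are looked at. After Week 12 that number depends on arm and, within the eltrombopag arm, on how long the child stays on drug. Those who need the drug longest are watched most closely. The planned comparison therefore mixes durability of response with frequency of testing.

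Temporary losses are foreseeable. Table 8C provides for counts below 30 by changing or restarting the dose, so a dip may be followed by recovery. Such a dip between common visits can be picked up by a monthly count on eltrombopag, whereas on standard therapy it is found only if an unscheduled visit happens to catch it. At stake is a fair reading of sustained response, which Section 1 presents as a possible advantage of eltrombopag.

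**Working it through.** The plan gives no loss rate, loss duration or power for this endpoint, so there is no figure of its own to reproduce. The 81.4% power statement concerns the primary endpoint only. The rates below are assumptions, shown as ranges.

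**1. Scheduled counts after Week 12**

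- Standard arm: 6 months and 1 year = 2.
- Eltrombopag, legible cells only: months 4, 5 and 7 added to the two common counts = 5.
- Eltrombopag, maximum: months 4–11 plus 1 year = 9. This requires footnote 7 to span all the monthly columns and the child to stay on drug all year. The platelet row is broken in the text available, so the months after 7 are inferred.

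**2. Detected loss with the same platelet process in both arms**

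Let each count meet the loss criterion with probability p. With independent counts, detected loss after k counts is 1 − (1 − p)^k. For p = 0.10:

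- k = 2: 1 − 0.9² = 19%
- k = 5: 1 − 0.9⁵ = 41%
- k = 9: 1 − 0.9⁹ = 61%

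Correlated counts were simulated from a first-order autoregressive normal series over months 4–12, cut at the p-th quantile:

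| p per count | Month-to-month correlation | Standard (2) | Eltrombopag (5) | Eltrombopag (9) |
|---|---|---|---|---|
| 10% | 0 | 19% | 41% | 61% |
| 10% | 0.5 | 19% | 35% | 50% |
| 10% | 0.8 | 18% | 28% | 35% |
| 5% | 0 | 10% | 23% | 37% |
| 5% | 0.5 | 10% | 20% | 30% |
| 5% | 0.8 | 9% | 15% | 21% |

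These figures apply to patients who have not already lost response by Week 12.

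**3. Dependence on how long a loss lasts**

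A second model gives both arms the same onset rate (0.03–0.10 per month from month 3) and the same mean duration. The ratio of detected losses, eltrombopag to standard, is:

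| Mean duration of loss | 9 vs 2 counts | 5 vs 2 counts |
|---|---|---|
| 2 weeks | 3.4–3.8 | 2.1–2.2 |
| 1 month | 2.5–2.8 | 1.7–1.8 |
| 2 months | 1.8–1.9 | 1.4 |
| 4 months | 1.4–1.5 | 1.2 |
| Permanent | 1.0 | 1.0 |

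For example, with onset 0.06 per month and mean duration 1 month, true loss is 42% in both arms. Detected loss is 29% (9 counts) or 19% (5 counts) against 11%. With an assumed 80 and 40 responders, all still at risk at month 3, a two-sided 5% test would reject about 62% of the time with 9 counts and 19% with 5, despite no true difference.

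**4. Adding losses in Weeks 1–12**

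These are seen on scheduled visits common to both arms, and a patient counts once. If a fraction e has already lost response by Week 12, total detected loss is e + (1 − e) × (detected loss among those at risk). With an assumed e = 0.40 in both arms and p = 10%:

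- Standard: 0.40 + 0.60 × 0.18 to 0.19 = about 51%.
- Eltrombopag, 5 counts: 0.40 + 0.60 × 0.28 to 0.41 = 57–65%.
- Eltrombopag, 9 counts: 0.40 + 0.60 × 0.35 to 0.61 = 61–77%.

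**5. Common schedule**

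With the same visits in both arms, identical loss processes give identical detected proportions (ratio 1.0), and the test keeps its nominal level.

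**The case against.** A reader might infer that eltrombopag must show more losses by design. The documents do not support that, for these reasons:

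- **Early losses are symmetric and may be many.** Section 1 says standard agents act only transiently, with counts falling within days to weeks. Many standard-arm losses should therefore occur by Week 12, on common scheduled visits. If early loss is higher on standard therapy, the gap narrows further or reverses.
- **Nine counts is a maximum.** Section 8.2.2.4 weans children who hold counts of 100 or more in 12.5 mg steps every 2 weeks. From 25 mg that is 2 steps (4 weeks) and from 75 mg 6 steps (12 weeks), so such children have few monthly counts. Those on drug all year are the ones who could not be weaned, and the assumption of equal loss processes fits them least well.
- **Other routes of detection exist.** Scheduled bleeding assessment does not differ by arm, and a symptomatic loss on standard therapy can prompt an unscheduled visit.
- **Durability has better endpoints.** The secondary endpoints in Sections 5.2.4 and 5.2.5 address need for treatment at 12 weeks and 6 months, and remission, resolution and stability at 1 year, at times common to both arms.

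All of this stands, and it limits the size and importance of the problem. It does not remove it. After Week 12 the number of scheduled looks still depends on arm, even on the narrowest reading of the schedule (5 against 2), and the exploratory label does not correct a known difference in detection.

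**Conclusion.** The concern holds as a detection bias, conditional on equal true temporary loss after Week 12. Its size among patients still at risk, at an assumed 10% per count, is 28–41% or 35–61% detected on eltrombopag against 18–19% on standard therapy. Once an assumed 40% early loss is included, it is 57–65% or 61–77% against about 51%. The bias is smaller with early weaning and with unscheduled detection in the standard arm, and nil for losses that last to 1 year.

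The direction of the observed difference also depends on the true loss rates, so the plan does not guarantee a result against eltrombopag. Nor do the primary or secondary conclusions depend on this endpoint. This is a low-priority but cheap improvement.

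**What to change.** In Sections 5.3.1 and 16.d, base the between-arm CMH test on assessments scheduled in both arms:

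- **Population:** patients who responded in the first 12 weeks.
- **Platelet criteria:** loss at any later common scheduled visit through Week 12, at 6 months, or at 1 year.
- **Bleeding criterion:** applied only where bleeding is scheduled in both arms, that is Weeks 1–4, Week 12 and 1 year, and not at 6 months.
- **All-counts version:** report loss at any time descriptively by arm, with the number of counts per patient.

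Keeping the visits through Week 12 matters: a test confined to 6 months and 1 year would discard the early losses, which both arms are equally scheduled to show.

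The cost is wording in two sections, with no new visits or data. The downside is that fewer loss events enter the test.
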